7. History of stroke or cerebrovascular accident within the last 6 months.
8. Recent history of major trauma (within 3 months).

9. Thrombocytopenia (<100,000/microL) or hyperkalemia (K > 5.2) on screening laboratory assay. May repeat lab value per PI discretion.
10. Untreated or poorly controlled hypertension (SBP > 150, DBP > 95), or hypotension (SBP <100 DBP <60)
11. Participant has hypothyroidism (TSH ≤(0.5mIU/L) or hyperthyroidism TSH ≥ 10mIU/L.
12. Participant has current infection (requiring prescription antimicrobial or antiviral medication, or hospitalization), or corticosteroid treatment (with the exception of inhaled or topical steroids) in the last 3 months prior to screening visit.
13. Participant is currently taking anti-inflammatory medication or has had anti-inflammatory medication within 1 week prior to screening (including over the counter formulations; e.g. Aleve, Motrin, ibuprofen, naproxen, low dose aspirin).
14. Participant has had surgery requiring > 2 days of hospitalization in the last 1 month prior to screening visit.
15. Participant has an active malignancy or autoimmune disease.
16. Participant has current significantly impaired liver function in the opinion of the study Medical Investigator (mild asymptomatic fatty liver is acceptable), or hepatic enzyme tests are ≥ 2.5 times normal limit.
17. Participant has a chronic, contagious, infectious disease, such as active tuberculosis, Hepatitis B or C, or HIV, per self-report.
18. Participant is an amputee and/or has presence of partial or full artificial limb.
19. Participant has had a significant cardiovascular event (e.g. myocardial infarction, stroke) ≤ 6 months prior to screening visit; or stated history of congestive heart failure; or participant has evidence of cardiovascular disease assessed during the ECG at screening. In the event of a positive stress test, participants are referred to their primary care physician. If the electrocardiogram (ECG) is determined to be a false positive, participant may be allowed to participate in study after confirmatory records obtained.
20. Participant currently has uncontrolled severe diarrhea, nausea or vomiting.

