College of Sports Medicine's (ACSM) Guidelines for Exercise Testing and Prescription. Heart rate, blood pressure and ECG, if applicable, will be recorded throughout this test. During the test, subjects will breathe through a low resistance mouthpiece and wear a nose clip. Expired gases will be measured by indirect calorimetry and heart rate monitored by a portable heart rate monitor and/or ECG.

Following a standardized warm up, subjects will begin exercising at a moderate intensity with the workload (resistance on a cycle ergometer or speed and grade on a treadmill) increased every minute until the subject can no longer continue. VO₂ max tests will take as little time as possible in order to ensure that test termination is due to the subject reaching VO₂ max rather than terminating the test due to muscle exhaustion. A leveling-off (plateau) or decline in oxygen uptake should be demonstrated in order to be reasonably sure that a subject has achieved the maximum capacity for aerobic metabolism. However, there are several additional criteria that will be used to determine if maximal aerobic capacity is achieved. These criteria are: the respiratory exchange ratio (RER) increased to 1.10 or higher and the subject's heart rate increased to within 10 beats of the age-predicted maximum (208 – [0.7 x age]).

The test will also be stopped, and subjects excluded from further participation if there is >2mm ST-segment depression on ECG or evidence of cardiovascular instability, such as hypotension, dangerous arrhythmias or angina.

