MR assessment of Intramuscular and Subcutaneous Fat (IMAT): Volumetric measurement of fat, muscle and bone in the participant’s mid-thigh leg will be completed using an Achieva 3T MRI/Multinuclear MRS (Philips, Andover MA). Scans will be performed under standardized conditions with subjects in a supine position. The torso XL coil will be placed around their legs (encompassing both knees and thighs). If the participant and the coil cannot fit into the bore of the magnet, the coil will be removed and the exam will be completed using the quadrature body coil. Each scan will take approximately 30 minutes to perform. Low resolution scans will be taken to determine the approximate midpoint of the participant’s femur. Then T1 weighted imaging sequences will be performed centered at the midpoint.

²Strength assessment. The initial weights for knee extension should be set based on the subject's predicted 1 repetition maximum (1 RM). Based on previous research, males and females < 65 years of age have a predicted 1 RM of 90% and 60% of their body weight, respectively, for the knee extension. For each additional 10 years of age the 1 RM should decrease 10% (ex. 91-year-old male would have a predicted 1 RM of 60% of his body weight). This number should be calculated and recorded on the data collection sheet. One can then calculate the subject's first 4 lifts at 20, 35, 50, and 70 percent of predicted 1 RM. This weight scale is followed, and weight is continually increased until termination of the test. If, prior to exercise, the blood pressure is less than 160/100 mm Hg, then the subject will warm-up on a bike for ~ 1 minute with no resistance. If BP is elevated the subject should rest for 3 more minutes. If BP is still elevated greater than 160/100 mm Hg, the subject will be sent home with the recommendation to contact their physician, and this subject will be followed up for potential re-testing.

Termination criteria for maximal strength testing:

- A subject asks to discontinue testing.
- An individual moves a weight through a full range of motion with relative comfort but cannot move through the full ROM with a two-unit increase.
- Subject cannot move through full ROM with proper form (subject lifts lower or upper back away from padded seat, subject kicks pad using acceleration force to lift weight, hands not crossed across chest, uneven or jerky ROM).

Relative termination criteria:

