and 180 degrees on each leg and gives a rating of P/D. Subject will perform three power tests on each leg and a 2 min rest between each increase in resistance. The subject will give a P/D rating after each trial. Before each test the tester will remind the subject to keep their back against the seat. If necessary other constant reminders will include – “Breathe normally,” “Look straight ahead,” or “Try to move your leg up to here (tester indicates end of movement).” The tester will also provide standard encouragement such as – “Move your leg as quickly as you can,” “Give me your best effort”. After both legs have been tested BP will be taken at conclusion of test and after 5-10 minutes of rest. If BP reading is normal, testing will continue. If it is above 160/100 mm Hg or has decreased by more than 15 mm Hg (top or bottom number) from the resting values, the subject will rest for 2 minutes and BP will be taken again. If BP has not normalized to below 160/100 mm Hg, further testing will be discontinued, and the subject will remain in the facility for at least ten more minutes while monitoring blood pressure. When BP finally normalizes, the subject will be sent home with the recommendation to contact their physician. The PI, [name], will also be notified.

Termination criteria for maximal power testing:

- A subject asks to discontinue testing.
- Equipment failure

Relative termination criteria:

- Subject reports >3 on the P/D scale (with explanation that the pain persists after the cessation of movement or if the subject reports >3 in any area besides the knee, upper or lower leg.

Before and after exercise activities are performed, the participant's blood glucose will be checked (type 2 diabetics only) using their home glucose monitor or glucose monitor at TRI. Blood glucose will be measured prior to and immediately following each exercise session for safety. If blood glucose is > 300 mg/dl, study team will notify TRI provider immediately for review of glucose values, as well as medications. If the glucose values are consistently > 400 mg/dl, participant will be instructed to follow up with their primary care physician. If blood glucose is < 100 mg/dl, a snack will be given, and the participant will be allowed to exercise. Self-monitored blood glucose measurements should be checked anytime a patient has symptoms of hypoglycemia or hyperglycemia.

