Muscle Biopsy. Muscle biopsies will be conducted by qualified staff following institutional policies and procedures including sterile techniques and sterile dressing to the site. Prior to the biopsies, participants will be asked for allergies including to lidocaine and the use of anticoagulants. Subjects allergic to lidocaine or that used anticoagulants in clinically significant amounts will be excluded. Sutures will be used to close the site, for those with a known allergy to steri-strips.

Optional Adipose Tissue Biopsy. Adipose biopsies will be conducted by qualified staff following institutional policies and procedures including sterile techniques and sterile dressing to the site. Prior to the biopsies, participants will be asked for allergies including to lidocaine and the use of anticoagulants. Subjects that have an allergy to lidocaine or have used anticoagulants in clinically significant amounts will be excluded. Sutures will be used to close the site, for those with a known allergy to steri-strips.

Oral Glucose Tolerance Test. All venipuncture will be conducted by qualified staff using aseptic technique.

Bidex/Strength testing/Exercise/Maximal Oxygen Consumption (VO_{2max}). Prior to conducting any exercise testing, a history and physical including ECG will be conducted and will be used to determine whether a subject is clear to participate in exercise testing. An MD/DO/NP/PA will be present during exercise testing for subjects who are at risk according to the American College of Sports Medicine (ACSM) Guidelines. ECG, blood pressure and heart rate may be monitored during the test.

Activity/Heart Rate Monitoring. Participants with nickel allergies will not be required to wear the monitor.

Bed Rest Intervention. During bed rest, the participants will be closely monitored by CRU nursing staff and medical oversight will be provided by [name], a physician/scientist with over 30 years of experience in conducting clinical investigations in diabetes and obesity.

Venous Thromboembolism. (VTE) risk mitigation. Individuals with prolonged immobility are at risk for VTE. We have used the American College of Chest Physicians (ACCP) Evidence Based Clinical Practice Guidelines in understanding the risk profile of enrolled participants for the development of venous thromboembolism as well as the risk of major bleeding with thromboprophylaxis.

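### Biodex testing: a blood-pressure fall of more than 15 mm Hg triggers a re-check, but the re-check has only an upper limit, so a fall that persists has no written action

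*Protocol*

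**What the plan says.** The rule is in the Protocol, Phase II – Pre-Bed Rest, note 2, in the paragraph on Biodex testing.

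- **Timing of the reading.** "After both legs have been tested BP will be taken at conclusion of test and after 5-10 minutes of rest".
- **Normal reading.** "If BP reading is normal, testing will continue". The text does not define normal.
- **Triggers for a repeat.** Either the reading is above 160/100 mm Hg, or it "has decreased by more than 15 mm Hg (top or bottom number) from the resting values, the subject will rest for 2 minutes", after which pressure is taken again.
- **Criterion for the repeat.** "If BP has not normalized to below 160/100 mm Hg, further testing will be discontinued". The same sentence requires a minimum of ten further minutes in the facility with blood pressure monitored.
- **Steps that follow.** Once pressure normalizes, the participant goes home with advice to contact a physician, and the principal investigator is told.

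The termination lists for power testing, directly below, cover the participant's request, equipment failure and, as a relative criterion, pain. They have no blood-pressure item.

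**The concern.** The procedure treats a fall in pressure as a warning sign and then does not say what to do if the fall persists. The trigger has two sides and the re-check has one. Read literally, the re-check clears a participant whom the same paragraph has just flagged as abnormal.

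What is at stake is participant safety. Both legs have been tested by the time pressure is read, so the exposure is any further testing in that session, plus loss of the monitoring, referral and notification steps. Participants are aged 60 to 80, and stable blood-pressure medication is permitted. The Potential Risks section names blood-pressure changes and fainting as risks of this kind of testing. The test is repeated after 10 days of bed rest, a stage at which the protocol itself schedules an orthostatic hypotension check. No primary outcome, power or error rate is affected.

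**Working it through.** The protocol gives no figure to reproduce. The check traces the rule and then places some readings against it.

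**The rule as written**

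- Repeat reading if: pressure above 160/100, OR systolic or diastolic more than 15 mm Hg below rest.
- Stop, monitor, refer and notify if: the repeat is not below 160/100.

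A persistent fall can satisfy the second line only if the other number is at or above its own limit (for example, systolic down 20 with diastolic at 102). In that case the upper limit is acting, not the fall.

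**How far a fallen value lies from the re-check limit**

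The Biodex paragraph asks only that pressure be in an acceptable range before exercise. The strength-test paragraph of the same note gives a number: "If, prior to exercise, the blood pressure is less than 160/100 mm Hg". Assume that this limit also defines the acceptable range for Biodex.

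| Resting value | After a fall of more than 15 | Margin under 160/100 |
|---|---|---|
| Below 160/100 (assumed entry limit) | systolic below 160 − 15 = 145, or diastolic below 100 − 15 = 85 | more than 15, either number |
| 150/95 (upper blood-pressure limit in Exclusion Criteria, item 10) | systolic below 150 − 15 = 135, or diastolic below 95 − 15 = 80 | systolic more than 160 − 135 = 25; diastolic more than 100 − 80 = 20 |

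The margins apply to the number that fell. Any such value sits well inside the re-check limit, so that limit cannot detect it.

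**Illustrative readings (assumed, not trial data)**

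| Rest | Repeat | Change | Below 160/100? | Written action |
|---|---|---|---|---|
| 130/80 | 110/70 | falls of 20 and 10 | yes | none |
| 130/80 | 95/55 | falls of 130 − 95 = 35 and 80 − 55 = 25 | yes | none |
| 130/80 | 165/95 | rises of 35 and 15 | no | stop, monitor, refer, notify |

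The second row is under the protocol's own exclusion limits, "hypotension (SBP <100 DBP <60".

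**How often the rule is used**

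The schedules of assessment mark Biodex/strength testing once before bed rest, once after it, once in the recovery phase and twice in optional Phase V: 1 + 1 + 1 + 2 = 5 sessions at most per participant.

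**Comparison within the protocol**

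The graded exercise test (Screening Visit 2, note 8) is to be stopped for "evidence of cardiovascular instability, such as hypotension, dangerous arrhythmias or angina". Hypotension is thus already accepted as a reason to stop one form of exercise testing, but that provision does not extend to Biodex.

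**The case against.** The strongest reply is that the paragraph, read as a whole, does not send a hypotensive participant on to more testing. Continuation is allowed only after a normal reading, a fall of more than 15 mm Hg is treated as not normal, and the later condition for going home refers to normalization without a number. A sensible clinician would probably stop. This stands in part: the protocol does not order testing to continue. But normal is undefined, and the only numeric target for the repeat is an upper one.

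The second reply is that exposure is small and other safeguards exist. The power test is over when pressure is read. Participants with hypotension are excluded at entry. Under Mitigation of Risks, history, physical examination and ECG precede exercise testing, a clinician attends for at-risk participants, and "ECG, blood pressure and heart rate may be monitored during the test". Coordinators are told to make the principal investigator aware of all events, adverse events are assessed at each visit, the orthostatic check precedes discharge after bed rest, and the investigator may withdraw anyone for safety. These points do lower the exposure, and the reporting duty weakens the argument about lost notification. However, each is an entry rule, a separate assessment, a provision for some participants only, optional, discretionary or after the fact. None says what a tester should do with a low repeat reading.

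Third, the graded exercise test is run until the participant cannot continue, so its stopping rules need not carry over to a short seated test. That is fair, and the point does not depend on it, because the Biodex paragraph sets its own 15 mm Hg trigger.

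Fourth, re-using 15 mm Hg could stop sessions without clinical need: rest at 150/80 settling at 134/80 is a fall of 16. This is a real cost of the simplest wording, and a lower limit fixed in advance by the medical investigator would avoid it.

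**Conclusion.** The point holds. For a blood-pressure fall that persists after Biodex testing, the protocol gives no written criterion for stopping, monitoring, referral or notification, although it treats the fall as a reason to re-check. The claim goes no further: the text does not instruct staff to continue.

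The trace of the rule needs no assumption. The 145/85 margins assume that the strength-test entry limit also governs Biodex, and the individual readings are illustrative. The documents give no frequency for persistent falls, so the number of participants affected cannot be estimated. The gap can arise at up to five sessions per participant. It should be corrected as a safety matter and has no bearing on the primary analysis.

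**What to change.** Replace the re-check sentence with a two-sided one, for example: If, on the repeat reading, blood pressure is not below 160/100 mm Hg, or either number is still more than 15 mm Hg below its resting value, further testing will be discontinued. Keep the same monitoring, referral and notification steps. If the medical investigator prefers a lower limit to the 15 mm Hg rule, state its value in the protocol.

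Use the same two-sided definition for the point at which pressure counts as normalized before the participant goes home. State that the rule applies at every Biodex session, including the one after bed rest.

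The cost is a sentence or two in the test procedure. A few sessions may end early and lose some later strength measurements. Strength is not among the primary outcomes named in Study Outcome Measures, which are leg lean mass, protein synthesis rate and mitochondrial respiration.

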Subjects who are not yet adults (infants, children, teenagers)

We are not enrolling participants who are not yet adults.

Cognitively Impaired Adults

We will not enroll cognitively impaired adults.

Adults Unable to Consent

We will not enroll adults who are unable to provide consent.

Documentation of Informed Consent Process

Documentation of the informed consent process is required to establish that the subject was accurately and adequately informed and that no study-related procedures were initiated prior to obtaining informed consent. A research team member will note in the source documentation the consent process, date consent was obtained, and that consent was obtained prior to initiating any research procedures. In the scenario of Remote Informed Consent Process documentation of all actions will be maintained as described in the

Investigator Guidance: Remote Inform Consent Process in Non-Except Research (HRP-831).

Waiver of Written Documentation of Consent or Waiver of Consent

N/A

Randomization

A randomization schedule containing the subject treatment group assignment (EX or CON) will be generated by the study statistician. A permuted blocks approach will be used with subjects stratified by gender. We will use blocks of random sizes of 4 to reach the total sample size of 20 to start (18 completers) in each group.

Study Visits

All study visits will be conducted at the AdventHealth Translational Research Institute.

[figure not shown]

Figure 1: Schematic depiction of the study protocol.

Phase	Description	Duration	Subject at home	Subject Ambulatory	Visit Window
I	Screening	< 35 days	Yes	Yes	35 days within PBR1
II	Pre-Bed Rest	5 days	Yes	Yes	-
III	Bed Rest	10 days	No	No	-
IV	Ambulatory/Exercise Recovery	4 weeks	Yes	Yes	\pm 1 days
V	Optional Resistance Exercise	4 weeks	Yes	Yes	\pm 2 days

Phase I – Screening.

Screening Visit 1

Approximate visit time: ~ 4 hours

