Our group has performed more than 1,500 muscle biopsies during the past 20 years (600 during the past 4 years since the move to the TRI), including same day serial biopsy studies and studies in men and women over 90 years old (14, 17-19, 34, 35). We will conduct 1 biopsy immediately post bed rest (day 10) and 4 biopsies of the vastus lateralis during the ambulatory or exercise recovery interventions. The approximate locations of the biopsies will be balanced as indicated to avoid interference from previous muscle biopsies (See Figure). A biopsy of the Vastus Lateralis muscle will be performed using the Bergstrom technique. Subjects will be placed in a supine position and the skin will be cleansed with chlorhexidine solution. After a sterile drape is placed over the skin, local anesthesia will be administered using lidocaine. The skin will be incised (approximately 0.5 cm) with a #11 scalpel, and the Bergstrom needle will be inserted into the Vastus Lateralis. Approximately 150 mg of muscle tissue will be obtained under suction. After the biopsy, pressure will be applied to stop bleeding and the skin will be closed with steri-strips (suture(s) if allergy to steri-strips). A sterile dressing will be applied. An MD, DO, NP, or PA will conduct this procedure. This procedure is well-tolerated in older adults. Subjects will not perform physical exercise 48 hours prior to the muscle biopsy to help prevent acute effects of exercise on muscle lipid and the other primary outcomes. Muscle specimens will be trimmed of any visible adipose and connective tissue using a dissecting microscope and processed. The following assays will be performed on the muscle biopsy specimens:

1. Mitochondrial respiration will be measured in permeabilized muscle fibers from vastus lateralis biopsies using the Oxygraph 2K system (Oroboros, Innsbruck, Austria). This approach permits a comprehensive evaluation of mitochondrial respiratory function upon titration with ETC complex-specific

inhibitors and substrates (56). We assess complex I+II supported respiration and palmitate β -oxidation supported respiration in separate assay protocols. Submaximal and maximal, coupled and uncoupled respiration will be evaluated along with coupling control ratios. This technique is well established in our laboratory (16, 19, 35) and we have conducted respirometry assays in over 500 muscle biopsy specimens in recent years.

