Exercise Recovery. The **exercise recovery program** will be supervised by a certified exercise physiologist and will take place at the TRI exercise training facility. Exercise compliance will be monitored carefully. We are examining the muscle specific effects of the recovery exercise program on the muscle groups of interest. We will use an exercise recovery program that has demonstrated substantial increases in quadriceps muscle size and strength in elderly people (37, 40, 105). During the 4 weeks of recovery, participants will perform a combination of aerobic and resistance exercise training with a certified exercise physiologist 3 days per week at the TRI exercise training facility. Exercise compliance and adherence will be monitored carefully. Aerobic training will be 30 minutes of brisk walking, jogging, cycle ergometry and will be at 60-80% of post bed rest VO₂max peak HR. Participants will wear a Heart Rate Monitor during Aerobic exercise sessions. Walking will be the primary mode of aerobic exercise given its widespread popularity and ease of administration across a broad segment of the older adult population. Three sets of 8–12 repetitions of each resistance exercise will be performed to target the major lower body muscle groups, including the vastus lateralis of the quadriceps.

Ambulatory Recovery. Participants in the ambulatory recovery group will not receive any exercise intervention or advice on exercise. Rather these participants will return to their regular daily routine that they engaged in prior to the bed rest intervention.

Participants in both Exercise and Ambulatory Recovery will be admitted to TRI the evening before Week 4 / Visit 16 for an overnight stay. The participants will be served dinner and type 2 diabetics will be asked to bring their own home glucometer to test glucose.

The following table summarizes the schedule of assessment during Ambulatory/Exercise Recovery Phase. Descriptions of assessments can be found above (Phase III).

Week Visit	Week 1				Week 2				Week 3				Week 4			
	1	2	3	4	5	6	7	8	9	10	11	12	13	14	15	16
Day of Week	F	M	T	Th	F	M	T	Th	F	M	T	Th	F	M	T	F
Window Days	+1	+1	+1	+1	+1	+1	+1	+1	+1	+1	+1	+1	+1	+1	+1	+3
Fasting Muscle Biopsy/Blood Draw ¹				X ^{**}				X ^{**}				X ^{**}				X ^{**}
Fasting Adipose Biopsy ² (optional)																X ^{**}
24-Hour Urine																X ^{**}
Glucose Clamp - 4Hr ⁶ with RMR																X ^{**}
Vital Signs	X*	X*	X*	X ^{**}	X*	X*	X*	X ^{**}	X*	X*	X*	X*	X*	X*	X*	X ^{**}

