Medication/Supplement Intake & Changes	X*	X*	X*	X ^{**}	X*	X*	X*	X ^{**}	X*	X*	X*	X*	X*	X*	X*	X ^{**}
Adverse Events	X*	X*	X*	X ^{**}	X*	X*	X*	X ^{**}	X*	X*	X*	X*	X*	X*	X*	X ^{**}
Metabolic Body Weight ¹⁶				X ^{**}				X ^{**}				X ^{**}		X ^{**}		X ^{**}
BIODEX/Strength Testing												X ^{**}				
Handgrip Strength												X ^{**}				
SPPB												X ^{**}				
Step Test												X ^{**}				
Questionnaires ²													X ^{**}			
DEXA				X ^{**}				X ^{**}				X ^{**}				X ^{**}
MR Assessments (ATPmax/IMCL/IMAT)				X ^{**}				X ^{**}				X ^{**}				X ^{**}

Accelerometer Handout															X*	X[^]
Accelerometer Collection						X*		X[^]								
VO _{2max} Test															X*[^]	
Cardio Exercise Program	X*	X*	X*		X*	X*	X*		X*	X*	X*		X*	X*	X*	
Strength Exercise Program	X*	X*	X*		X*	X*	X*		X*	X*	X*		X*	X*	X*	
Deuterated H ₂ O administration ⁸	X*[^]		X*[^]	X*[^]	X*[^]											
400m Walk Test															X*[^]	

* = only on this visit for exercise cohort

[^] = only on this visit for ambulatory cohort

Phase V – Optional Resistance Training.

Following Phase IV of the study, to expedite complete recovery, subjects may attend three resistance exercise training sessions per week over a four-week period, for a total of 12 visits. Resistance exercise training will include weight training of all major muscle groups. Subjects will perform three sets of eight repetitions at 70-80% of their 1 RM for each exercise, which will include upper body and lower body muscle groups. During all exercise sessions, subjects must be supervised by qualified personnel with the appropriate training to identify if the subject is under any type of distress. Study assessments will also be performed during the 4-week resistance training according to the table below:

Assessment	Resistance Training (Optional)											
	Week 1			Week 2			Week 3			Week 4		
	1	2	3	4	5	6	7	8	9	10	11	12
Vital Signs	X	X	X	X	X	X	X	X	X	X	X	X
Medication/supplement intake and changes	X	X	X	X	X	X	X	X	X	X	X	X
Adverse events	X	X	X	X	X	X	X	X	X	X	X	X
Metabolic Body Weight ¹⁶			X			X			X			X
Resistance Training ¹	X	X	X	X	X	X	X	X	X	X	X	X
BIODEX/Strength Testing	X											X
Handgrip Strength						X						X
SPPB						X						X
Step Test						X						X
Questionnaires ²						X						X
Accelerometer Collection		X										

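### The Phase IV visit windows permit a training session within 48 hours of the week 1-3 biopsies, against the protocol's own exercise-free interval

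*Protocol*

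**What the plan says.** Three places in the Protocol bear on this.

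- **Phase III, note 1 (Muscle Tissue Biopsy):** "Subjects will not perform physical exercise 48 hours prior to the muscle biopsy to help prevent acute effects of exercise on muscle lipid". The same sentence extends the purpose to the other primary outcomes.
- **Phase IV schedule of assessments:** the visit days for visits 1-16 are "Day of Week F M T Th F M T Th F M T Th F M T F" and the windows are "Window Days +1 +1 +1 +1 +1 +1 +1 +1 +1 +1 +1 +1 +1 +1 +1 +3". The row "Fasting Muscle Biopsy/Blood Draw" is marked at visits 4, 8, 12 and 16. The cardio and strength training rows are marked at the other visits, for the exercise cohort only.
- **Study Visits, phase table:** the Phase IV row reads "Ambulatory/Exercise Recovery 4 weeks Yes Yes \pm 1 days", which is not the window in the schedule.

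Study Outcome Measures names leg lean mass, protein synthesis rate and mitochondrial respiration as primary outcomes, measured after bed rest and at recovery weeks 1 to 4. No text ties a biopsy visit to the date of the last session, gives clock times for sessions or biopsies, or says which Phase IV window governs.

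**The concern.** The 48-hour rule is the protocol's safeguard against reading the after-effect of a single bout as an effect of training. In weeks 1-3 the schedule meets it with nothing to spare, and the windows then let the session and the biopsy move independently. Staff who follow the visit table could log a biopsy as in window although it breaks the rule.

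Training sessions exist only in the exercise arm. Any residue of the last session would therefore not cancel between arms. It would enter the EX-CON comparison at particular weeks, and the trial's stated aim is to describe how the response unfolds over time.

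**Working it through.** **Inputs.** Required interval: 48 h (biopsy note). Last session before each biopsy: Tuesday (visits 3, 7, 11, 15). Biopsy: Thursday in weeks 1-3, Friday in week 4. Windows: +1 day for visits 1-15 and +3 days for visit 16 (Phase IV schedule), or plus or minus 1 day for every visit (phase table).

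**Nominal days.** Tuesday to Thursday is 2 days (48 h at equal clock times). Tuesday to Friday is 3 days (72 h). The unshifted schedule just meets the rule in weeks 1-3 and has a day to spare in week 4.

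**With windows.** Let s be the shift of the session and b the shift of the biopsy, in days. The gap is 2 + b - s in weeks 1-3 and 3 + b - s in week 4.

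| Window used | Weeks | s | b | Gap, days | Combinations under 2 days |
|---|---|---|---|---|---|
| Phase IV schedule | 1-3 | 0, 1 | 0, 1 | 1 to 3 | 1 of 4 |
| Phase IV schedule | 4 | 0, 1 | 0, 1, 2, 3 | 2 to 6 | 0 of 8 |
| Phase table | 1-3 | -1, 0, 1 | -1, 0, 1 | 0 to 4 | 3 of 9 |
| Phase table | 4 | -1, 0, 1 | -1, 0, 1 | 1 to 5 | 1 of 9 |

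The one short combination under the Phase IV schedule is s = 1, b = 0 (Wednesday session, Thursday biopsy): 2 + 0 - 1 = 1 day, about 24 h. If both visits move by one day, the gap returns to 2 + 1 - 1 = 2 days. These fractions count permitted combinations. They are not probabilities of a breach.

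**Clock time (assumption).** The protocol requires a fast of at least 8 hours before biopsy but gives no hour. If the biopsy is at 08:00 Thursday and an unshifted session is at 14:00 Tuesday, the gap is 10 + 24 + 8 = 42 h. With the same biopsy hour, sessions at 09:00, 12:00 and 16:00 leave 47, 44 and 40 h. A session at 08:00 leaves 48 h, and one at 07:00 leaves 49 h.

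**Which outcomes are exposed.** Mitochondrial respiration is assayed on the biopsy and is the primary outcome most clearly exposed. Protein synthesis is read from deuterated water given across the four recovery weeks, so the hour of the last bout matters less. Leg lean mass is not a biopsy measure. The muscle lipid and phospho-signalling assays also use the biopsy. They are not among the outcomes named under Study Outcome Measures, although the biopsy note's wording treats muscle lipid as primary.

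**The case against.** The best reply is that the 48-hour rule is mandatory and covers every biopsy. A visit window is a scheduling tolerance and does not cancel an explicit prohibition. The nominal days comply, and the biopsy visit has its own +1 day, so a site can already move it when the session moves. This stands as far as it goes: the windows permit a breach and do not compel one. It does not settle the matter, for two reasons. The two stated windows differ. And moving a Thursday biopsy to Friday puts it on the day of the next training visit (5, 9 or 13), with no rule for which comes first.

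A reader might infer several stronger things that the document does not support.

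- *That unshifted biopsies fall short of 48 hours.* This depends wholly on assumed clock times.
- *That all the primary outcomes are contaminated.* Only mitochondrial respiration is clearly exposed.
- *That only the exercise arm exercises near a biopsy.* This is true of training. But the Phase IV table, as extracted, marks a VO2max test and a 400 m walk at visit 15 for both arms. It also appears to put strength testing at visit 12, a biopsy day, for both arms, though column alignment there is uncertain.
- *That the longer week-4 gap is itself a fault, or that the week-4 clamp is compromised.* The rule sets a minimum and concerns biopsies. Under the Phase IV schedule, week 4 never falls below two days.
- *That the case report form lacks the needed data.* The form is not shown, and days since the last session could be derived from visit dates.

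**Conclusion.** The point holds as a scheduling inconsistency that can defeat a stated safeguard. Under the Phase IV schedule's windows, three of the four recovery biopsies (weeks 1-3) can be in window about 24 h after training. Under the phase table's window the minimum is 0 days in weeks 1-3 and 1 day in week 4. These day counts need no assumption beyond the stated days and windows. Any shortfall on unshifted days is an assumption about clock times.

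If a breach occurs through training, it occurs in the exercise arm only and would act mainly on mitochondrial respiration and the other biopsy assays. Neither the frequency of breaches nor the size of any bias can be computed from the document. The change is worth making because it is cheap and removes an avoidable one-sided error. It is not a ground for doubting the design as a whole.

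**What to change.** Reconcile the biopsy note, the Phase IV schedule and the phase table:

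1. State one Phase IV visit window and use it in both tables.
2. Make the biopsy window at visits 4, 8, 12 and 16 conditional on the protocol's own 48-hour interval, counted from the end of the last completed exercise session or exercise test. If that session or test moves, the biopsy moves with it.
3. State that a training visit due on the same day as a biopsy follows the biopsy.
4. Record the time since last exercise at each biopsy, in both arms, if this is not already captured.

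The cost is a few sentences of protocol text and at most one data field. Scheduling freedom shrinks slightly. The DXA and MR assessments listed at the same visits may also shift by a day.
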